### **5.2.9 Inexact Values**

In the case where a variable is recorded as “> x”, “ $\geq$  x”, “ $<$  x” or “ $\leq$  x”, a value of x will be taken for analysis purposes. The inexact value, inclusive of the symbol, will be reported in the listings.

### **5.2.10 Electrocardiogram (ECG) Data**

For ECG data recorded on continuous scales, triplicate values recorded at a time point will be averaged and rounded to the integer for summarization purposes. For the overall interpretation, the

most severe (worst case) of the replicate readings will be taken (separately for the central reader and the investigator assessment).

### **5.2.11 Vital Signs**

For blood pressure (both systolic and diastolic) and pulse rate, the orthostatic changes will be calculated as standing minus sitting readings.

A patient will be defined to have orthostatic hypotension if either or both of the below criteria are met:

- a decrease of > 20 mm Hg in systolic blood pressure in measurements from supine to standing
- a decrease of > 10 mm Hg in diastolic pressure in measurements from supine to standing

Temperatures reported in Fahrenheit will be converted to Celsius for reporting using the following formula:

$$\text{Celsius} = (\text{Fahrenheit} - 32)/1.8$$

Weights reported in pounds will be converted to kilograms using the following formula:

$$\text{Kilograms} = \text{pounds} * 0.453592$$

Heights and waist circumferences reported in inches will be converted to centimeters using the following formula:

$$\text{Centimeters} = \text{inches} * 2.54$$

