- 15. Patients with uncontrolled hypertension (diastolic blood pressure [DBP] >95 mmHg or systolic blood pressure [SBP] >145 mmHg in any position) or symptomatic hypotension, or orthostatic hypotension defined as a decrease of ≥20 mmHg in SBP and/or a decrease of ≥10 mmHg in DBP after at least 3 minutes standing compared with the previous supine blood pressure, OR development of symptoms. NOTE: Blood pressure measurements may be repeated once to ensure reproducibility of the exclusionary result(s) before excluding a patient based on the criteria noted above.
- 16. Patients with known ischemic heart disease or any history of myocardial infarction, congestive heart failure (whether controlled or uncontrolled), angioplasty, stenting, or coronary artery bypass surgery.
- 17. Patients with epilepsy or a history of seizures (with the exception of febrile seizure).

Physical and Laboratory Results

18. Patients with a positive urine drug screen or a positive blood alcohol test. Detectable levels of marijuana, barbiturates, benzodiazepines or opiates in the drug screen are not exclusionary if, in the Investigator's documented opinion, the patient does not meet DSM-5 criteria for substance abuse or

Confidential Page 10 of 102

- dependence, in the Investigator's documented opinion, the positive test does not signal a clinical condition that would impact the safety of the patient or interpretation of the trial results, and approval was granted by the Medical Monitor prior to treatment.
- 19. Patients with a history of alcohol use disorder, substance use disorder (by DSM-5 criteria) within 12 months of Screening or a positive screen for drugs of abuse at Screening (unless consistent with current prescription for medical condition).
- 20. The following laboratory test results are exclusionary:
 - Platelets $\leq 75,000/\mu L$ or $\leq 75 \times 10^9/L$
 - Hemoglobin $\leq 9 \text{ g/dL or } \leq 90 \text{ g/L}$
 - Neutrophils, absolute $\leq 1000/\mu L$ or $\leq 1 \times 10^9/L$
 - AST >2 × ULN
 - ALT >2 × ULN
 - Creatine phosphokinase >3 × ULN, unless discussed with and approved by the Medical Monitor
 - Creatinine $\geq 2 \text{ mg/dL or } \geq 176.8 \mu\text{mol/L}$
 - Estimated neytrine clearance of <45 mL/min, calculated using the Cockcroft-Gault equation, at Screening
 - HbA1c \geq 7.0%
 - Abnormal free T4 (during Screening), unless discussed with and approved by the Medical Monitor (Note: Free T4 will be measured only if the result for TSH is abnormal).

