- 15. Patients with uncontrolled hypertension (diastolic blood pressure [DBP] >95 mmHg in any position or systolic blood pressure [SBP] >145 mmHg) or symptomatic hypotension, or orthostatic hypotension defined as a decrease of ≥20 mmHg in SBP or a decrease of ≥10 mmHg in DBP after at least 3 minutes standing compared with the previous supine blood pressure, OR development of symptoms. NOTE: Blood pressure measurements may be repeated once to ensure reproducibility of the exclusionary result(s) before excluding a patient based on the criteria noted above.
- 16. Patients with known ischemic heart disease or any history of myocardial infarction, congestive heart failure (whether controlled or uncontrolled), angioplasty, stenting, or coronary artery bypass surgery.
- 17. Patients with epilepsy or a history of seizures (with the exception of febrile seizure).

Physical and Laboratory Results

- 18. Patients with a positive urine drug screen or a positive blood alcohol test. Detectable levels of marijuana, barbiturates, benzodiazepines or opiates in the drug screen are not exclusionary if, in the Investigator's documented opinion, the patient does not meet DSM-5 criteria for substance abuse or dependence, in the Investigator's documented opinion, the positive test does not signal a clinical condition that would impact the safety of the patient or interpretation of the trial results, and approval was granted by the Medical Monitor prior to treatment.
- 19. Patients with a history of alcohol use disorder, substance use disorder (by DSM-5 criteria) within 12 months of Screening or a positive screen for drugs of abuse at Screening (unless consistent with current prescription for medical condition).
- 20. The following laboratory test results are exclusionary:
 - Platelets $\leq 75,000/\mu L$ or $\leq 75 \times 10^9/L$
 - Hemoglobin $\leq 9 \text{ g/dL or } \leq 90 \text{ g/L}$
 - Neutrophils, absolute $\leq 1000/\mu L$ or $\leq 1 \times 10^9/L$
 - AST >2 × ULN
 - ALT $>2 \times ULN$
 - Creatine phosphokinase >3 × ULN, unless discussed with and approved by the Medical Monitor
 - Creatinine $\geq 2 \text{ mg/dL or } \geq 176.8 \mu\text{mol/L}$
 - Estimated creatinine clearance of <45 mL/min, calculated using the Cockcroft-Gault equation, at Screening

Confidential Page 41 of 102

- HbA1c $\geq 7.0\%$
- Abnormal free T4 (during Screening), unless discussed with and approve by the Medical Monitor (Note: Free T4 will be measured only if the result for TSH is abnormal)

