### 5.13.3 Vital Signs

Descriptive statistics for observed values and changes from baseline in the following vital signs will be presented by treatment group and visit:

- Systolic blood pressure (mmHg)
- Diastolic blood pressure (mmHg)
- Pulse rate (bpm)
- Body temperature (degrees Celsius)
- Body weight (kg)

In addition, a separate table presenting BMI and waist circumference will also be provided. A listing will be provided including all measurements.

For blood pressure and pulse rate, the orthostatic changes will be calculated as standing minus sitting readings. At each visit, the number of patients meeting the criteria for orthostatic hypotension as described in Section 5.2.11 will be summarized. Orthostatic changes will be listed separately, including a flag to identify cases of hypotension.

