14.3.2	Listings of Deaths, Other Serious and Significant Adverse Events		
14.3.2.1	Deaths – Safety Analysis Set	IP	
14.3.2.2	Serious Adverse Events – Safety Analysis Set	IP	
14.3.3	Narratives of Deaths, Other Serious and Certain Other Significant Adverse Events		
14.3.4	Abnormal Laboratory Values		
14.3.4	Abnormal Laboratory Values – Safety Analysis Set	IP	
14.3.5	Extent of Exposure, Dosage Information, And Compliance		
14.3.5.1	Treatment Exposure – Safety Analysis Set	IP	
14.3.5.2	Treatment Compliance – Safety Analysis Set	IP	
14.3.6	Vital Signs and Physical Examination		
14.3.6.1	Vital Signs – Safety Analysis Set	IP	
14.3.6.2	BMI and Waist Circumference – Safety Analysis Set	IP	14.3.6.1

Table Number	Table Title	Validation Method	Shell Number (if repeat)
14.3.6.3	Incidence of Orthostatic Hypotension – Safety Analysis Set	IP	
14.3.6.4	Physical Examination – Safety Analysis Set	IP	
14.3.6.5	Shift Table of Physical Examination to Day 28 – Safety Analysis Set	IP	
14.3.7	Other Safety		
14.3.7.1	Hematology – Safety Analysis Set	IP	14.3.6.1
14.3.7.2	Shift Table of Hematology – Safety Analysis Set	IP	
14.3.7.3	Chemistry – Safety Analysis Set	IP	14.3.6.1
14.3.7.4	Shift Table of Chemistry – Safety Analysis Set	IP	14.3.7.2
14.3.7.5	Urinalysis – Safety Analysis Set	IP	
14.3.7.6	Coagulation – Safety Analysis Set	IP	14.3.6.1
14.3.7.7	Hormones – Safety Analysis Set	IP	14.3.6.1
14.3.7.8	12-Lead ECG – Safety Analysis Set	IP	
14.3.7.9	Shift Table of 12-Lead ECG – Safety Analysis Set	IP	
14.3.7.10	Columbia – Suicidal Severity Rating Scale (C-SSRS) – Safety Analysis Set	IP	
14.3.7.11	Summary of Simpson-Angus Scale (SAS) Total Score – Safety Analysis Set	IP	
14.3.7.12	Summary of Abnormal Involuntary Movement Scale (AIMS) Total Score – Safety Analysis Set	IP	14.3.7.11
14.3.7.13	Summary of Barnes Akathisia Rating Scale (BARS) Global Score – Safety Analysis Set	IP	14.3.7.11
14.3.8	Concomitant Medication		
14.3.8	Concomitant Medications by ATC Level 2 and Preferred Name – Safety Analysis Set	IP	14.1.3.3
14.4	PK Tables		
14.4.1	Serum Concentrations, Descriptive Statistics – Pharmacokinetic Analysis Set	IP	
14.4.2	PK Parameters, Descriptive Statistics – Pharmacokinetic Analysis Set	IP	
14.4.3	Dose-Proportionality, Power Model Analysis – Pharmacokinetic Analysis Set	Stat IP	
14.5	PD Tables		
14.6	Other Data		

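### The SAP flags orthostatic hypotension at strict cut-offs (>20/>10 mmHg), the protocol defines the same term with inclusive ones (≥20/≥10), and the change listed beside the flag uses another reference position

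*SAP*

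**What the plan says.** SAP 5.2.11 (Vital Signs) flags orthostatic hypotension when at least one of two conditions is met: "a decrease of > 20 mm Hg in systolic blood pressure in measurements from supine to standing" or "a decrease of > 10 mm Hg in diastolic pressure in measurements from supine to standing". SAP 5.13.3 then states that, at each visit, "the number of patients meeting the criteria for orthostatic hypotension as described in Section 5.2.11 will be summarized". The output is Table 14.3.6.3, "Incidence of Orthostatic Hypotension", in the Safety Analysis Set.

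The protocol defines the term in one place only, exclusion criterion 15, which is printed twice. Section 5.2 has "orthostatic hypotension defined as a decrease of ≥20 mmHg in SBP or a decrease of ≥10 mmHg in DBP". The synopsis has "a decrease of ≥20 mmHg in SBP and/or a decrease of ≥10 mmHg in DBP after at least 3 minutes standing". Both compare standing with the previous supine reading. Both also count the development of symptoms and allow one repeat measurement before a patient is excluded.

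On the listed change, SAP 5.2.11 says that for blood pressure and pulse rate "the orthostatic changes will be calculated as standing minus sitting readings", and 5.13.3 repeats this. 5.13.3 adds: "Orthostatic changes will be listed separately, including a flag to identify cases of hypotension".

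**The concern.** The two definitions share the term, the numbers and the two body positions. They differ in the inequality, and neither the SAP amendment log nor SAP Section 8 (changes from the protocol) mentions it. The difference matters only at the boundary, but readings in whole mmHg can fall exactly there. A patient who would be kept out of the trial for a given fall would not be counted as a case if the same fall occurred on treatment.

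Protocol 1.8.1 names falls from low blood pressure among the risks of the drug class, and the SAP gives orthostatic hypotension its own incidence table. A reader would expect the term in that table to mean what it means in the protocol.

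Separately, the listing prints a standing-minus-sitting change next to a flag derived from supine to standing, so the printed change does not explain the flag.

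**Working it through.** **Step 1: the two rules.** Let S and D be the systolic and diastolic falls from supine to standing in mmHg.

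- Exclusion 15, blood pressure limb: S ≥ 20 or D ≥ 10.
- SAP flag: S > 20 or D > 10.

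Every patient who meets the second rule meets the first, so the SAP count is equal or lower in any data set. The rules differ only where S ≤ 20 and D ≤ 10 with at least one equality.

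**Step 2: boundary cases.**

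| Supine | Standing | Fall S/D | Exclusion 15 cut-off | SAP flag |
|---|---|---|---|---|
| 120/80 | 100/75 | 20/5 | met | no |
| 120/80 | 112/70 | 8/10 | met | no |
| 120/80 | 100/70 | 20/10 | met | no |
| 120/80 | 99/80 | 21/0 | met | yes |
| 120/80 | 101/71 | 19/9 | not met | no |

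**Step 3: possible size (illustration only).** The documents give neither the distribution of orthostatic changes nor the reading precision, so every input here is assumed. The supine-to-standing change was taken as bivariate normal with SBP-DBP correlation 0.5 and rounded to the stated step, with no entry criterion applied. The gap is the first share minus the second; the share missed is the gap divided by the first share.

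| SBP change, mean (SD) | DBP change, mean (SD) | Step, mmHg | Flagged by ≥ | Flagged by > | Gap, points | Share of ≥ cases missed |
|---|---|---|---|---|---|---|
| -2 (9) | +2 (6) | 1 | 4.84% | 3.53% | 1.31 | 27.1% |
| -4 (10) | 0 (7) | 1 | 12.72% | 10.14% | 2.58 | 20.3% |
| -6 (12) | -2 (8) | 1 | 24.72% | 21.20% | 3.52 | 14.2% |
| -2 (9) | +2 (6) | 2 | 5.62% | 2.98% | 2.64 | 47.0% |
| -4 (10) | 0 (7) | 2 | 14.18% | 8.98% | 5.20 | 36.7% |
| -6 (12) | -2 (8) | 2 | 26.51% | 19.48% | 7.03 | 26.5% |

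A wider grid used SBP mean 0, -3, -6, -10 with SD 8, 10, 12; DBP mean -2, 0, 2, 4 with SD 6, 7, 8; and SBP-DBP correlation 0.3, 0.5, 0.7. That is 4 × 3 × 4 × 3 × 3 = 432 settings of 200,000 patients, with supine and standing readings each rounded to 1 mmHg. Patients who met the exclusion 15 cut-offs on a single screening reading were removed, with within-patient correlation 0.3 or 0.6 (432 × 2 = 864 settings). Results:

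- flagged by ≥: 1.4% to 27.4%;
- flagged by >: 0.9% to 23.8%;
- gap: 0.5 to 3.9 points (median 2.2);
- share of ≥ cases missed: 12% to 36% (median 21%).

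Repeating the grid with 2 mmHg readings gave a gap of 1.0 to 7.9 points.

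**Step 4: the listed change.** Take SBP 130 supine, 115 sitting, 108 standing. The flag uses 130 - 108 = 22 > 20, so it is positive. The listed change is 108 - 115 = -7. Replacing sitting by supine in the listed change gives 108 - 130 = -22, which explains the flag. The flag rate does not change, because the flag already uses supine.

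**The case against.** The strongest reply is that the two cut-offs need not match. Exclusion 15 decides who enters; the flag describes readings on treatment. The protocol sets no on-treatment definition, and its Section 10.4.5.4 plans only summary statistics and changes from Baseline for vital signs. QTcF also has different limits for entry (>450 msec) and for stopping (>500 msec or a rise of >60 msec). This stands to a degree: the SAP does not depart from a planned protocol analysis. But those QTcF limits are visibly different rules for different decisions. Here the same term, numbers and positions are reused and only the inequality changes, without explanation.

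Second, inclusive limits in the flag would not fully unify the term, because exclusion 15 also has a symptom limb and a permitted repeat reading. That is correct; the change aligns only the blood pressure limb.

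Third, symptomatic or clinically noteworthy falls are recorded as adverse events (Protocol 8.2.2 and 9.2.1) and enter the TEAE tables (SAP 5.13.1). This limits the harm. An asymptomatic fall of exactly 20 or 10 that no one judges noteworthy would still be in neither place, except as raw readings in a listing.

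Fourth, the simulated sizes rest wholly on assumptions, and the main range also fixes precision at 1 mmHg. That stands: the percentages illustrate and do not estimate.

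Finally, the sitting/supine mismatch is display only, and the flag can be checked from the listed readings. This also stands, which is why it is secondary.

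**Conclusion.** The point holds as a minor inconsistency. One term has two blood pressure cut-offs across the documents, and the stricter one governs on-treatment counting. From the text alone only the direction is certain: the incidence in Table 14.3.6.3 is equal to or lower than under the entry cut-offs. The size is unknown. The illustrative 0.5 to 3.9 points per visit depends on the assumed distributions and on 1 mmHg readings, and coarser readings widen the gap.

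The consequence is limited. The table is descriptive, the rule is the same in every arm, all readings are listed, and vital signs in the Phase 1 study of healthy volunteers were largely unchanged (Protocol 14.2.1). The primary endpoint, power and type I error are not affected. The listing mismatch is real and internal to the SAP, but has no effect on incidence.

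**What to change.** Reconcile the flag in SAP 5.2.11 with the blood pressure limb of exclusion 15 so that the term has one cut-off, for example by using inclusive inequalities (≥20 and ≥10) in the flag. State there that the flag does not include the symptom limb.

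In SAP 5.2.11 and 5.13.3, compute the listed orthostatic change as standing minus supine, and keep standing minus sitting as an extra column if it is wanted.

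The cost is SAP wording, one derived flag and one listing column. Supine, sitting and standing readings are all collected already (Protocol 8.2.2). With inclusive limits the reported incidence may be somewhat higher.

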### **5.2.12 Positive and Negative Symptoms Scale (PANSS)**

The PANSS is a questionnaire consisting of 30 items, divided in 3 subscales (negative symptoms, positive symptoms, and general psychopathology), where each item (representing a symptom construct) can be rated with a value ranging from 1 to 7. The total score is obtained by summing the scores for each item/symptom, and similarly the sub-scale scores are obtained by summing the scores of the individual items included in each of them.

In addition to this, PANSS Marder factor scores are defined as a further combination of the items, using the mapping described in Table 4. The scores for each factor are obtained by summing up the scores of each individual item listed in the table below for the respective factor.

**Table 4** PANSS Marder Factors Mapping

Factor Name	Items
Negative Symptoms	Blunted affect Emotional withdrawal

	Poor rapport Passive social withdrawal Lack of spontaneity Motor retardation Active social avoidance
Positive Symptoms	Delusions Hallucinatory behavior Grandiosity Suspiciousness Stereotyped thinking Somatic concern Unusual thought content Lack of judgement and insight
Disorganized Thought	Conceptual disorganization Difficulty in abstract thinking Mannerism and posturing Poor attention Disturbance of volition Preoccupation Disorientation
Uncontrolled Hostility/Excitement	Excitement Hostility Uncooperativeness Poor impulse control
Anxiety/Depression	Anxiety Guilt Tension Depression

### 5.2.13 Columbia-Suicide Severity Rating Scale (C-SSRS)

The following outcomes are C-SSRS categories and have binary responses (yes / no). The categories have been re-ordered from the actual scale to facilitate the definition of composite endpoints:

Category 1	Wish to be Dead
Category 2	Non-specific Active Suicidal Thoughts
Category 3	Active Suicidal Ideation with Any Methods (Not Plan) without Intent to Act
Category 4	Active Suicidal Ideation with Some Intent to Act, without Specific Plan
Category 5	Active Suicidal Ideation with Specific Plan and Intent

Category 6	Preparatory Acts or Behavior
Category 7	Aborted Attempt
Category 8	Interrupted Attempt
Category 9	Actual Attempt (non-fatal)
Category 10	Completed Suicide

Suicidal Ideation since baseline – A “yes” answer at any time during double blind treatment to any one of the 5 suicidal ideation questions (categories 1-5) on the C-SSRS.

Suicidal Behavior since baseline – A “yes” answer at any time during double blind treatment to any one of the 5 suicidal behavior questions (categories 6-10) on the C-SSRS.

There will be no imputation of missing data for C-SSRS.

#### **5.2.14 Clinical Global Impression – Severity (CGI-S)**

The CGI-S assesses the physician/investigator’s assessment of the severity of the patient’s illness, using a 7-point rating scale ranging from 1 (= normal, not at all ill) to 7 (= among the most extremely ill patients).

A patient will be classified as a responder on the CGI-S if they provide a score of either 1 (= normal, not at all ill), 2 (= borderline mentally ill) or 3 (=mildly ill).

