5.1 Inclusion Criteria

Patients will be eligible for inclusion in the study if they meet all of the following criteria:

- 1. Patient, who is able to provide written informed consent (as required by Institutional Review Board [IRB]) prior to the initiation of any protocol-required procedures. Ability, in the opinion of the PI, to understand the nature of the trial and follow protocol requirements, including the prescribed dosage regimens, tablet ingestion, and discontinuation of prohibited concomitant medication, and to be reliably rated on assessment scales.
- 2. Must be willing to be hospitalized for the duration of the inpatient period of the study, and willing to comply with instructions from the Investigator and study staff.
- 3. Have stable living environment when not in hospital, as demonstrated by the ability to provide contact information for themselves or family/friend(s)/caregiver(s).
- 4. Male and female patients 18 to 55 years of age inclusive at the time of informed consent with a diagnosis of schizophrenia as defined by Diagnostic and Statistical Manual of Mental Disorders, Fifth Edition (DSM-5) criteria and confirmed by the MINI 7.0.2 for Schizophrenia and Psychotic Disorders Studies.
- 5. BMI must be \geq 18 and \leq 40 kg/m².

Confidential Page 37 of 102

6. Patient who is:

• experiencing an acute exacerbation of psychotic symptoms, with onset ≤6 weeks before Screening AND the patient requires hospitalization for this acute exacerbation of psychotic symptoms.

OR

- if already an inpatient at Screening, has been hospitalized for onset ≤2 weeks for the current exacerbation.
- 7. Patients who are experiencing an acute exacerbation of psychotic symptoms and marked deterioration of usual function as demonstrated by meeting ALL of the following criteria at the Screening and Baseline visits:
 - Total PANSS score between 80 and 120, inclusive, and
 - Score of ≥4 (moderate or greater) for ≥2 of the following Positive Scale (P) items: Item 1 (P1; delusions), Item 2 (P2; conceptual disorganization), Item 3 (P3; hallucinatory behavior), Item 6 (P6; suspiciousness/persecution), and
 - CGI-S score ≥4 (moderately to severely ill).
- 8. Have received previous antipsychotic treatment (dose and duration as per the label) and who showed a previous good response to such antipsychotic treatment (other than clozapine) in the last 12 months, according to the Investigator's opinion.

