
 
• Taking a prohibited medication prior to Week 4
 
• Starting an emergency treatment prior to Week 4
 
 
All of these intercurrent events (ICEs) will be handled via a composite strategy, i.e. patients will be considered as non-responders
	
Missing data at Week 4 because of discontinuation due to ‘Lack of Efficacy’ or a drug-related AE will be imputed as non-responders. For all other missing data, the PANSS total score imputed for the primary analysis of the primary endpoint will be dichotomized as responders or not.
 
As a sensitivity analysis, all missing data will be imputed as non-responders.

Population-level summary measure	Analysis approach
Difference between patients treated with LB-102 (50 or 75 mg QD) and those treated with matching placebo in the PANSS response rate at Week 4 post-baseline.	
This endpoint will be analyzed using a logistic regression model including treatment and Baseline PANSS score as covariates to estimate the odds ratio (OR) of response of LB-102 (50 or 75 mg QD) vs placebo. The model will be fit separately to all imputed datasets and results pooled across imputations to obtain one single treatment effect estimate alongside 95% CI.
 
The same model will also be fit for the sensitivity analysis and a single OR (alongside its 95% CI).

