#### **5.11.5.1 Change from Baseline to Week 4 in the CGI-S score**

The change from Baseline in the CGI-S score will be analyzed using a similar MMRM as the one for the primary endpoint, replacing baseline CGI-S as covariate in the model. Similar quantities (LS means and their differences, with 95% CIs and p-values) will be presented. Descriptive summaries of observed and change from Baseline values will be presented for all treatment arms.

CGI-S response, defined as a CGI-S score  $\leq 3$ , will also be analyzed separately for each time-point, categorizing any patient with missing data as a non-responder. The number of patients meeting this definition will be summarized descriptively on the mITT analysis set with counts and percentages, including approximate Wald-type 95% CI (with a continuity correction). The difference between treatment arms in the above defined responder rate will be analyzed by reporting the estimated difference in proportions alongside its 95% Wald-type 95% CI with a continuity correction as well as the  $P$ -value derived from Fisher's exact test (using a Monte Carlo approximation to deal with the large sample size). Example SAS code is provided below:

```
ods output RiskDiffCol2 = diff FishersExact = fisher;
proc freq data = ;
  by atptn;
  tables trt01pn*avalc / riskdiff (column = 2 cl = (wald(correct))) chisq;
  exact fisher / mc seed = 123;
run;
```

For the derivation of the exact p-value, it is assumed that the 2x2 table for each visit has the following form:

Treatment	Non-Response	Response
LB-102	a	b
Placebo	c	d

Under the above structure, Fisher's test as implemented in PROC FREQ is defined based on the value  $a$  in the first row/column and the associated one-sided p-values support different alternative hypotheses (the null being that of independence between row and columns):

- Left-sided p-value: supports the alternative that the probability of a patient treated with LB-102 of being a non-responder is smaller than what would be expected under the independence null;
- Right-sided p-value: supports the alternative that the probability of a patient treated with LB-102 of being a non-responder is larger than what would be expected under the independence null.

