Since the hypothesis we're interested in is that patients treated with LB-102 are more likely to be responders than non-responder, a small left-sided p-value supports this hypothesis and as such this is the p-value that will be reported in the table. All CGI-S data will also be listed.

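### CGI-S response is compared between arms without adjustment for baseline CGI-S, which decides how far a patient must improve to respond; the comparison is valid but gives up a modest amount of precision

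*SAP*

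**What the plan says.** Protocol 5.1, inclusion criterion 7, requires "CGI-S score ≥4 (moderately to severely ill") and applies this to patients "meeting ALL of the following criteria at the Screening and Baseline visits". SAP 5.2.14 describes CGI-S as rated "using a 7-point rating scale ranging from 1 (= normal, not at all ill) to 7" and defines response by the score alone: "A patient will be classified as a responder on the CGI-S if they provide a score of either 1", 2 or 3.

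SAP 5.11.5.1 says that response "will also be analyzed separately for each time-point, categorizing any patient with missing data as a non-responder". The comparison is a difference in proportions with a Wald interval and Fisher's exact test. The sample code is "tables trt01pn*avalc / riskdiff (column = 2 cl = (wald(correct))) chisq", run by time-point, with no baseline term or stratum. On the reported p-value it says that "a small left-sided p-value supports this hypothesis and as such this is the p-value that will be reported in the table".

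The neighbouring analyses do use baseline. CGI-S mean change is analysed by MMRM with baseline CGI-S as a covariate (SAP 5.11.5.1). For PANSS response, SAP 2.3, Table 2 says: "This endpoint will be analyzed using a logistic regression model including treatment and Baseline PANSS score as covariates".

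CGI-S response is not among the endpoints in Protocol 3.2 or SAP 2.2.2, although the table list in SAP section 10 labels it a secondary efficacy endpoint (Table 14.2.2.1.2).

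**The concern.** The lowest eligible baseline score and the highest responding score are adjacent integers, so the same label covers different amounts of improvement. Baseline category is therefore prognostic for response, and it is already recorded for every eligible patient. An unadjusted two-by-two comparison ignores it. No stratification factor is named in the readable text of Protocol 6.3 or SAP 4, so nothing stated in the design or in this analysis corrects a chance difference between arms in the share of baseline-4 patients.

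CGI-S response is also the exception within the SAP. When site was dropped from the PANSS response model over separation, baseline PANSS stayed. The amendment log explains the current CGI-S response method only by computational trouble with exact calculations, which is not a reason to leave baseline out. At stake are the width of the interval and the reading of a displayed secondary result, not the primary conclusion.

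**Working it through.** **Inputs from the documents.** Entry CGI-S of 4 or more at Screening and Baseline (Protocol 5.1); response at 3 or less (SAP 5.2.14); scale 1 to 7. The plan states no CGI-S response rate or power, so there is no figure to reproduce. It gives no baseline CGI-S distribution, change SD or rater reliability, so everything from step 2 on rests on assumptions.

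**1. Improvement needed.** Categories needed = baseline - 3, which is 1, 2, 3 and 4 for baseline 4, 5, 6 and 7.

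**2. Response by baseline category.** Simulation assumptions: latent severity normal, mean 4.6 or 4.9, SD 0.6; each rating is latent severity plus error (SD 0.4 to 0.6), rounded; patients kept if Screening and Baseline ratings are both 4 or more; true change with mean -0.5 and SD 0.8 on placebo. Response is 31% to 38% at baseline 4, 16% to 23% at 5 and 5% to 13% at 6. A typical case (latent mean 4.9, error SD 0.5) gives about 32%, 18% and 8%, with eligible patients split about 26/50/24 over 4, 5, and 6 or more.

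**3. Precision.** With baseline shares w and response rates p_b, and overall rate p, the large-sample variance ratio of the stratified to the unadjusted risk difference is approximately

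sum of w·p_b·(1 - p_b), divided by p·(1 - p).

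Typical case:
- p = 0.26×0.32 + 0.50×0.18 + 0.24×0.08 = 0.192, so p(1 - p) = 0.155.
- Within strata: 0.26×0.32×0.68 + 0.50×0.18×0.82 + 0.24×0.08×0.92 = 0.0566 + 0.0738 + 0.0177 = 0.148.
- Ratio = 0.148/0.155 = 0.953, a cut of about 5%.

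Over the assumed latent means and error SDs, with true-change SD 0.8, the cut is:
- 2.6% to 4.3% at mean change 0;
- 3.7% to 6.8% at -0.5;
- 4.5% to 9.0% at -1.0.

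That is about 4% to 7% at -0.5, and about 2% to 9% overall. Since √0.96 = 0.980 and √0.93 = 0.964, a 4% to 7% cut narrows the interval by about 2% to 4%.

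The figure depends on the model. A smaller true-change SD raises it: with SD 0.5 it is 4.8% to 8.9% at -0.5. A cruder model treats the recorded baseline as exact: P(response) = Φ((3.5 - b + m)/s), with mean improvement m = 0.5 and SD of change s = 1.0. It gives 50%, 15.9% and 2.3% at baseline 4, 5 and 6. With a 25/65/10 mix, p = 0.230, p(1 - p) = 0.177 and the within-stratum sum is 0.0625 + 0.0869 + 0.0022 = 0.152, a cut of about 15%. That model has no regression to the mean, so it overstates the gradient and is best read as an upper illustration.

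**4. Chance imbalance, no drug effect.** Suppose one arm has 10 points more of its patients at baseline 4 and 10 points fewer at 5.
- Simulated rates: 0.10×(0.32 - 0.18) = 1.4 points of spurious difference.
- Cruder model: 0.10×(0.500 - 0.159) = 3.4 points at m = 0.5; 0.10×(0.691 - 0.309) = 3.8 points at m = 1.0.
- Identical baseline mix: 0.

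**The case against.** The strongest reply is that nothing here is wrong. Randomisation balances baseline category in expectation, the standard error already reflects chance imbalance, and the unadjusted test keeps its error rate. Any absolute-state endpoint depends on starting severity. The listed CGI-S endpoint is mean change, which is baseline-adjusted. Protocol 10.4.4.3 treats secondary p-values as descriptive. Finer strata may also be sparse at early visits. All of this stands. It limits the point to a small gain in efficiency and consistency; it does not remove a gain that costs almost nothing.

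A reader might infer something stronger: that the definition lets rating noise drive response, that one-category movers dilute the contrast, or that there is no minimum change and no confirmation. The documents do not support these readings.
- Entry at 4 or more already forces at least a one-category drop.
- With no true change, the assumed rating error alone gives only about 1% to 6% responders.
- Protocol Table 7.1, footnote h, provides central review of CGI-S at Screening, Baseline and final endpoint.
- In simulation, also requiring a 2-point drop loses about 4 to 5 points of power, so one-category movers carry net signal.
- Day 28 is the last scheduled CGI-S, so Week 4 response could not be confirmed at a later visit.

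**Conclusion.** The point holds as a modest inefficiency and an internal inconsistency. It is not an error in the definition or a bias. CGI-S response depends on baseline category by construction, and its comparison omits baseline while the SAP adjusts the two closest analyses. The likely loss is about 4% to 7% of variance at a placebo change of -0.5 and about 2% to 9% across the main scenarios. A 10-point imbalance between categories 4 and 5 would go uncorrected and could move the difference by roughly 1 to 4 points.

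These sizes rest on assumed CGI-S distributions; the threshold arithmetic and the missing adjustment come from the documents. It would be wrong to conclude that the planned comparison is invalid or that the responder rate is mostly noise. No confirmatory decision depends on this result.

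**What to change.** In SAP 5.11.5.1, keep response as a score of 3 or less and keep missing as non-response. For each active arm against placebo, at each time-point, report a Mantel-Haenszel risk difference with 95% CI and p-value, stratified by baseline CGI-S (4, 5, 6 or more). State whether the p-value is one- or two-sided. Fix before unblinding a rule for collapsing sparse strata, for example merging 6 or more into 5. This matters most at early visits and for the 100 mg arm, which the 3:3:3:1 allocation makes a third the size of the others. The unadjusted difference and Fisher's test may stay as supportive.

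The cost is a paragraph of SAP text, a stratum variable in the existing code and a revised table shell. No new data are needed. A companion row requiring a 2-point decrease is not needed for this correction.
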